1.4. Sample Size Justification

The study will enroll 600 subjects between the ages of 13 and 85 years, inclusive. Subjects will be randomized 1:1 to one of the treatment arms.

The sample size is based on the primary endpoint of the hospital recovery scale at Day 6. Based on the proportional odds model and assuming a benefit of approximately 38% reduction of the common odds ratio, a total sample size of 600 subjects (randomized 1:1) is required to obtain a power of 90% [11]. Inclusion of stratification factors would provide some improvement on the derived power.

In the sample size calculation it is assumed that the distribution of subjects treated with placebo in combination with SOC treatment will be as follows on Day 6:

- Not hospitalized: 30%
- Non-ICU hospitalization, not requiring supplemental oxygen: 30%
- Non-ICU hospitalization, requiring supplemental oxygen: 25%
- Admitted to the ICU, not requiring invasive mechanical ventilation: 5%
- Requiring invasive mechanical ventilation: 5%
- Death: 5%

This sample size is robust to mild to moderate changes in this distribution.

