5.1. Analysis Specifications

5.1.1. Level of Significance

The population used for the evaluation at the final analysis will depend on the outcome scenario of the interim analysis: i.e.; scenario 1: continue with the full study population or scenario 2: continue only with the subjects with an onset of symptoms less than 72 hours before first study drug intake. Tables/graphs/listings will account for the selected scenario.

As a confirmatory strategy, to account for multiplicity in the statistical evaluation of the most important efficacy endpoints, in either scenario, a combination of hierarchical testing and the Bonferroni-Holm testing procedure will be applied to control for the overall Type I error rate at the 5% level. The following endpoints are included in the confirmatory strategy:

1. Hospital recovery scale at Day 6, ie, primary endpoint
2. Incidence in post-baseline complications
3. Time to hospital discharge
4. Time from ICU admission to ICU discharge
5. Time to return to daily activities
6. Time from start of mechanical ventilation to end of mechanical ventilation
7. Rate of re-hospitalization

First, the primary endpoint will be tested for superiority of pimodivir in combination with SOC over placebo in combination with SOC at the 2-sided 5% significance level.

The confirmatory test procedure follows the Serial Gate Keeping strategy as outlined in Section 7 of the FDA's draft guidance on Multiple Endpoints to control the overall type I error at the 5% 2-sided level. The primary and six most important secondary endpoints (listed above) will be tested in the hierarchical order per the 5 steps outlined below. All alphas and p-values specified are 2-sided.

Step 1: Test the primary hypothesis ("Hospital recovery scale at Day 6")

- If the p-value is $\leq 5\%$, continue to Step 2.
- If the p-value is $> 5\%$, stop testing, and no claim will be made.

Step 2: Test first set of 2 secondary endpoints (“Incidence in post-baseline complications” and “Time from start of study drug to hospital discharge”). The Bonferroni-Holm procedure will be applied to control the type I error within Step 2.

- If the smallest of the 2 p-values is $\leq 2.5\%$ and the largest of the 2 p-values is $\leq 5\%$, continue to Step 3.

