- Non-ICU hospitalized on the day of assessment (including readmittance), not ready for discharge during the whole day of assessment, as judged by the investigator and supplemental oxygen is required by the subject
- In the ICU but there is no medical reason to be in the ICU during the day of assessment, and supplemental oxygen is required by the subject

Requiring supplemental oxygen is defined by:

- Receiving supplemental oxygen through a face mask or nasal cannula and not being able to sustain a blood oxygen saturation of $\geq 94\%$ when breathing room air for 15 minutes at any time on the day of assessment.
- If supplemental oxygen was provided chronically pre-influenza infection (based on medical history), that amount of supplemental oxygen is exceeded to prevent hypoxia, tachypnea or dyspnea at some point on the day of assessment.
- Not receiving supplemental oxygen and either:
 - Having a blood oxygen saturation of $< 94\%$ when breathing room air for 15 minutes at any measurement on the day of assessment, or
 - In case of known pre-influenza $SpO_2 < 94\%$ (e.g., due to COPD), the current blood oxygen saturation on room air is lower than pre-influenza infection levels by at least 3%.

2. Non-ICU hospitalization, not requiring supplemental oxygen

Subject met either of the 2 following criteria:

- Non-ICU hospitalized on the day of assessment (including readmittance) and not ready for discharge during the whole day of assessment, as judged by the investigator
- In the ICU but there is no medical reason to be in the ICU during the day of assessment

1. Not hospitalized

Any of the following:

- Discharged from the hospital before the day of assessment
- Hospitalized at the day of assessment but ready for discharge on both the day of assessment and the day prior, as judged by the investigator (e.g., in case of lack of bed availability in a skilled nursing facility, lack of social support at home).

Notes: If a subject was discharged from the hospital “Against Medical Advice” on the day prior to the day of assessment, the subject will be considered as hospitalized (evaluating the other aspects of the HRS to define the correct category based on available data, e.g.: requiring supplemental oxygen, on the day of assessment). The hospital recovery scale category will be considered missing on subsequent days.

The HRS will be missing after a subject withdrew (except for withdrawal due to death) from the study.

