5.3. Major Secondary Endpoints

5.3.1. Definition

Formulae to be used for derived variables, including data conversions, are provided in the tables below.

Note that for time-to event variables the actual date or times that the endpoint is met will be used. For the time-to-event variables, in case of death prior to the event, the subject will be censored using a time-to equal to the maximum time across all subjects.

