5.3.1.1. Clinical Outcome

Measurement	Formula
Time to hospital discharge (hours) [Time-to event]	
The time from first study drug intake to first hospital discharge (=event) in hours. Note this excludes time in hospital because of re-hospitalization (a new hospitalization is considered as a re-hospitalization if there is at least 1 day in between the start date of the new hospitalization and the end date of the previous hospitalization) and hospitalizations that ended before first intake.
 
Subjects who complete or withdraw from the study while still hospitalized will be censored at the date of completion or withdrawal. If the time is not available they will be censored at 23:59.
 
If time of end of hospitalization is not known but we have a date of discharge then time will be imputed at 23:59.
 
(Date and time of event or censoring-- date and time of first dose of study drug)/3600, rounded to one decimal.

Time to readiness for hospital discharge (days) [Time-to event]	
The time from first study drug intake until the time to readiness for hospital discharge (= event) in days, with readiness for hospital discharge defined by the investigator. In case at the date of discharge the subject is not ready to be discharged as per investigator assessment, the discharge readiness day will be set to the next day.
 
Censoring of the time will be done analogous to “Time to hospital discharge”, only using the date information, as time is not available for the event.

Total length of hospital stay (hours) [Duration]	
The total number of hours a subject stayed in the hospital during the period from first study drug intake until study termination, calculated as sum of [(end date and time of hospitalization-- start date and time of first intake)/3600], rounded to one decimal for all separate hospital stays per subject. If the time is not available it will be put at 23:59
 
If hospitalization started before first study drug intake, then datetime of first study drug will be used.
 
If hospitalization is still ongoing at study end, the end date and time will be imputed by the end date and time of the last phase as defined in table 1.

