ICU admission started post-baseline	
Incidence of post-baseline ICU admission
 
 - Admitted to ICU post-baseline - Not admitted to ICU post-baseline 
Note: In case a patient is in the ICU at baseline and (after discharge from the ICU) the patient is re-admitted post-baseline, this subject will be counted as "Admitted to ICU post-baseline".

First admission to intensive care unit (ICU)	
When was the subject first admitted to the ICU during the study?
 
Categories:
 
 - In ICU at baseline - Admitted in ICU Post-baseline - Never admitted to ICU
Time from ICU admission to ICU discharge (hours) [Time-to event]	
The time from max(first admission to ICU, first study drug intake) until the time of first discharge from the ICU.
 
Censoring and calculation of the time will be done analogous to "Time to hospital discharge".
 
Only subjects admitted to the ICU (at any point during the trial) are included in the analysis and analysis is restricted to the first ICU admission.

Time from ICU admission requiredness to ICU discharge readiness (days) [Time-to event]	
The date from max(requiring ICU level of care , first study drug intake) until the date of not requiring ICU anymore(= event), requiring ICU level of care to be defined by the investigator.
 
Censoring and calculation of the time (days) will be done analogous to "Time to hospital discharge"
 
Subjects that do not require ICU level of care will be excluded from this analysis and this analysis is restricted to the first required ICU level of care.

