
Time from start of mechanical ventilation to end of mechanical ventilation (hours) [Time-to event]
	
The time from max(start date and time of first mechanical ventilation, study drug intake) until the end date and time of mechanical ventilation.
 
Note: Invasive and non-invasive mechanical ventilation are considered and are defined on the Oxygen Supplementation form: Type of supplemental oxygen administration. Only the first mechanical ventilation period is considered.
 
Censoring and calculation of the end time will be done analogous to “Time to hospital discharge” if time part of the start of mechanical ventilation is missing then it will be imputed with 00:00.
 
Subjects that are not on mechanical ventilation (at any point during the trial) are excluded from this analysis and this analysis is restricted to the first time mechanical ventilation is used.

Total time on mechanical ventilation (hours) [Duration]
	
The total number of hours of mechanical ventilation during the period from first intake until study termination, calculated as sum of [(end date and time of mechanical ventilation – start date and time of mechanical ventilation)/3600], rounded to one decimal for all separate events per subject
 
In case mechanical ventilation was started before first intake or in case the start datetime of mechanical ventilation is missing, then the date and time of first intake will be used.
 
In case mechanical ventilation ended after the end of the trial or in case the end datetime of mechanical ventilation is missing, then the end datetime of last contact date will be used.
 
If time of the start of mechanical ventilation is missing, then use 00:00. If time of the end of mechanical ventilation is missing, then use 23:59. The derivation of the total time is analogous to “Total length of hospital stay”.

Time to clinical response (hours) [Time-to event]
	
The time to clinical response is defined as the time (in hours) from first study drug intake until the first assessment (actual date and time) of a successive series of 4 recordings (over 5 scheduled successive analysis timepoints, 1 missing timepoint is allowed) where at least 4 of 5 symptoms (temperature, blood oxygen saturation, heart rate, SBP, respiration rate) are normalized, with at least normalization of temperature and blood oxygen saturation.
 
Normalization of clinical response is defined in Table 4.

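### Endpoints 6 and 4 score the first end of ventilation and the first ICU discharge as success without requiring that the subject is alive and stays off support

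*SAP*

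**What the plan says.** SAP 5.3.1.1 defines three of the alpha-controlled secondary endpoints by a first exit.

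- **Endpoint 6, mechanical ventilation.** The clock starts at the later of first ventilation and first study drug and stops when ventilation ends. Invasive and non-invasive ventilation (NIV) both count, and "Only the first mechanical ventilation period is considered".
- **Endpoint 4, ICU.** The time runs "until the time of first discharge from the ICU", for the first admission only.
- **Endpoint 3, hospital discharge.** The event is the first discharge. A new stay is a re-hospitalization only "if there is at least 1 day in between the start date of the new hospitalization and the end date of the previous hospitalization".

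The ICU and ventilation rows refer their censoring and time calculation back to the hospital-discharge row by analogy. SAP 5.3.1 adds one rule for all time-to-event variables: "in case of death prior to the event, the subject will be censored" at the maximum time across subjects.

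For discharge against medical advice on the previous day, the notes to the hospital recovery scale (HRS) in SAP 5.2.1 say that "the subject will be considered as hospitalized". The scale is then missing on later days. Attachment 6 (Case 4) gives the data pattern.

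**The concern.** An end of support is good news only if the subject survives and does not soon need the support again. The definitions of endpoints 6 and 4 contain neither condition, and the death rule does not act once an exit has been recorded.

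The same SAP is stricter elsewhere. Clinical response needs four recordings over five timepoints, NEWS2 of 2 or less must last 24 hours, and return to daily activities needs two successive recordings. The SAP also foresees ICU readmission and a second ventilation episode, but uses them only in incidence tables and total durations.

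At stake is the meaning of two confirmatory claims. If exits that are not recovery are scored as early events, a treatment that prevents deaths among ventilated subjects can lose much of its advantage in the Gehan-Wilcoxon test, which gives early events the most weight. Endpoint 3 has a separate inconsistency: the same against-advice discharge is a favourable event there and not a recovery on the primary scale.

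**Working it through.** **1. The plan's own figure.** SAP 1.4 states, "assuming a benefit of approximately 38% reduction of the common odds ratio", that "a total sample size of 600 subjects (randomized 1:1) is required to obtain a power of 90" per cent. For ordered categories with 1:1 allocation:

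N = 12(z₀.₉₇₅ + z₀.₉₀)² / [ln(OR)² × (1 − Σp̄ᵢ³)]

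Here p̄ is the mean of the placebo distribution (30/30/25/5/5/5%) and that distribution shifted by OR = 0.62 (40.9/29.9/19.4/3.4/3.3/3.2%).

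- 12 × (1.960 + 1.2816)² = 126.09
- ln(0.62)² = 0.2285
- Σp̄ᵢ³ = 0.0825
- N = 126.09 / (0.2285 × 0.9175) ≈ 601.4, and power at 600 is 89.9%

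The figure reproduces. It does not depend on this point, and the documents give no sample size, power or event count for endpoints 3, 4 or 6.

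**2. Tracing subjects through the text.**

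- *Dies while ventilated or in the ICU:* death precedes the event, so the subject is censored at the maximum. Protected.
- *Ventilation stopped, death hours later:* the event has already occurred, so the death rule does not apply. Scored as early success.
- *Stop time equal to death time:* precedence is not stated.
- *Extubated, then re-intubated:* event at the first extubation, unless the one-day gap rule carries over from the hospital row.
- *ICU exit, then readmission:* as for re-intubation. *ICU exit, then death:* event at the exit.
- *NIV, then intubation:* depends on what a period is, which the SAP does not define.
- *Discharged against advice:* event for endpoint 3; on the HRS, hospitalized the next day and then missing.

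**3. Size of the ventilated subset (assumed).** The nearest documented figure is the placebo Day 6 invasive-ventilation cell: 5% × 300 = 15 subjects. The simulations use 30 per arm (10% of 300) and a range of 15-60.

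**4. Lost benefit.** Assumed: ventilated mortality 45% placebo, 20% pimodivir, and half of deaths preceded by a stop. Two independently coded simulations (1,500 runs with true median ventilation of 8 days; 3,000 runs with separately chosen timing) give the chance of significance in favour of pimodivir:

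| Per arm | Alive and ventilator-free | As written |
|---|---|---|
| 15 | 20% | 7% |
| 30 | 36-40% | 10% |
| 60 | 65% | 18% |

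With mortality of 30% against 20% and 30 per arm, the figures are about 9% and 3-4%. The as-written figures depend on when stops occur; earlier stops cost more.

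**5. Bias toward an arm.** Assumed: 30 per arm; identical lognormal recovery times (median 120 h, log-SD 0.8); maximum 672 h; non-recovery exits at a median of 24 h; 4,000 runs. The test is an unstratified Mann-Whitney, which equals Gehan-Wilcoxon when all censoring is at the common maximum.

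- Exits in 20% of both arms: significant for pimodivir 2.5%, for placebo 2.5%. No inflation.
- Exits in 40% pimodivir, 20% placebo: 20.6% for pimodivir as written, against 0.1% if those exits are censored at the maximum. With exits at a median of 72 h the as-written figure is 6.6%.
- Same 40% against 20%, over 15-60 per arm: 12-36% (24 h exits) or 5-10% (72 h exits).

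If the only non-recovery exit is a stop before death (half of deaths; stops at a median of 3-6 days), a harmful drug with mortality of 45% against 20% is favoured in 0.6-1.4% of trials, below the nominal 2.5%.

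Stratification and the interim combination test were not simulated.

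**The case against.** **The gap rule may already apply.** The ICU and ventilation rows point back to the hospital-discharge row, which contains the one-day gap. On that reading, rapid re-intubation and quick ICU return fall within one period. This has force, so it would be wrong to say flatly that the SAP has no joining rule. But the reference covers censoring and calculation of time; it does not say that the definition of a new episode is imported. Even if it is, it does nothing for death after an exit.

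**NIV followed by intubation.** A reader might infer that escalation to a tube is scored as success. The text does not support that as a finding. Both types are mechanical ventilation, so one continuing period is the more natural reading. Separate administration types on the form leave room for the other reading, so this is an ambiguity. Simulated false-benefit rates of 24-26% assume that escalation scores as an event and occurs in 30% of pimodivir against 10% of placebo subjects; they are not relied on here.

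**Gatekeeping.** SAP 5.1.1 sets the testing sequence "to control the overall type I error at the 5% 2-sided level". Endpoint 4 is reached only after endpoints 1-3 succeed, and endpoint 6 only after 1-5. The primary scale ranks ventilation and death worst, so a drug that worsens them is unlikely to get that far. This limits how often the problem matters, but not what a claim would mean once reached.

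**Equal stop and death times.** Protocol 10.3 makes death an automatic withdrawal, and the hospital row censors withdrawals. That is a plausible route to the maximum time, but it is not stated.

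**Visible elsewhere.** Total ICU and ventilation time, mortality, clinical failure and the daily HRS would show deterioration. None of these is in the confirmatory sequence.

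**Conclusion.** Endpoints 6 and 4 lack a survival and persistence condition, and the death rule covers only death before the event. The demonstrated consequence is dilution of a true benefit. With 30 ventilated subjects per arm, mortality of 45% against 20%, and half of deaths preceded by a stop, power is about 36-40% under a sustained, alive definition and about 10% as written. Every one of these inputs is assumed; the documents supply none.

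A reader might go further and infer that the type I error is inflated, or that a harmful drug would generally look beneficial. The calculations do not support that. Equal exit rates produce no inflation, and bias toward an arm requires such exits to be more frequent there. Even then it depends on timing and on the balance with deaths censored at the maximum.

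The endpoint 3 inconsistency for against-advice discharge is clear from the text, but its frequency is unknown and its effect was not computed. A readiness-based version is planned, but it counts a not-ready discharge as an event one day later, so it does not remove the conflict.

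This should be fixed, but given the gatekeeping it does not threaten the primary analysis.

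**What to change.** In the ventilation and ICU rows of SAP 5.3.1.1:

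1. State that ventilation records of any type, and likewise ICU records, separated by less than a fixed gap (for example 24 h) form one period. This also settles NIV followed by intubation and whether the hospital gap rule carries over.
2. Define the event as the first time the subject is alive and free of all mechanical ventilation (or out of the ICU) for at least that window.
3. Censor at the maximum time any subject who dies without meeting this, including when the stop time equals the death time.

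For endpoint 3, reconcile against-advice discharge (the Attachment 6 Case 4 pattern only) with the HRS. At a minimum, add a sensitivity analysis that does not count these discharges as events. How to censor them is the sponsor's choice. Keep the next-day readiness rule for other not-ready discharges: Attachment 6 Cases 1, 3 and 8 are not-ready discharges labelled as not against advice, and removing the rule altogether could take away their event.

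The cost is SAP wording and programming on data already collected, settled before unblinding. The downside is slightly fewer and later events.

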 - Cardiovascular and cerebrovascular disease (eg, myocardial infarction, congestive heart failure, arrhythmia, stroke)
 - Muscular disorders (eg, myositis, rhabdomyolysis)

-
- Central nervous system [CNS] involvement
 - Acute exacerbation of chronic kidney disease
 - Decompensation of previously controlled diabetes mellitus
 - Other infections (eg, sinusitis, otitis)
 - All-cause mortality.
 - Incidence and duration of antibiotic treatment.
 - The number (proportion) of subjects needing extended treatment.
 - The number (proportion) of subjects requiring re-hospitalization.
 - The number (proportion) of subjects not hospitalized at Day 6.
 - Time to clinical response. Clinical response is defined as achieving 4 of the 5 following vital sign resolution criteria, including at least the fever and oxygen saturation criteria, maintained for at least 24 hours:
 - having no fever (without the use of antipyretics within 8 hours),
 - oxygen saturation of at least 94% without oxygen supplementation or return to pre-influenza infection oxygen saturation (in patients with a known pre-influenza oxygen saturation level <94%),
 - improved respiratory status (a respiratory rate ≤ 24 breaths per min without supplemental oxygen or return to pre-influenza infection supplemental oxygen requirement in patients with chronic oxygen use),
 - heart rate 100 beats per minute or lower,
 - systolic blood pressure of 90 mmHg or higher without inotropic support given within 2 hours of assessment.
 - Time to respiratory response. Respiratory response is defined as achieving the following 2 criteria for at least 24 hours:
 - improved oxygen saturation of at least 94% without oxygen supplementation (return to pre-influenza infection oxygen saturation in patients with a known pre-influenza oxygen saturation level <94%) and
 - improved respiratory status characterized by a respiratory rate ≤ 24 breaths per min without supplemental oxygen or return to pre-influenza infection supplemental oxygen requirement in patients with chronic oxygen use.
 - PK parameters of pimodivir (ie, plasma concentration just prior to the beginning or at the end of a dosing interval [C_{trough}], C_{max} , t_{max} , and AUC_{12h}), as determined by population PK analysis.
 - Time to viral negativity by qRT-PCR and viral culture.
 - Viral load over time by qRT-PCR and viral culture.
 - The emergence of viral resistance against pimodivir detected by genotyping and/or phenotyping.
-

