	
Only vital signs assessments performed during hospitalization (excluding measurements during re-hospitalization) and up to Day 14 (during hospitalization) or Day 19 (for subjects with extended treatment during hospitalization) will be taken into account to determine time to clinical response. Assessments taken after hospital discharge or after Day 14 or Day 19 (for subjects with extended treatment), whichever comes first, will not be taken into account. In case there was more than one hospitalization period, only assessments of the first hospitalization period will be used.
 
In case clinical response is not met, data will be censored. Censoring will be done as follows
 
 1) Last non-missing record in the applicable period indicate normalization (but insufficient recordings to meet the time to clinical response criteria) 
Censoring will be done at the first record of normalization
 
 2) Last non-missing record in applicable period does not indicate normalization 
Censoring will be done after the last observation of vital signs recordings, which is 13:00 on the same day if the last observation was a morning assessment (from 3:01 until 11:00), 21:00 if the last observation was an afternoon assessment (from 11:01 until 19:00), 5:00 the next day if the last assessment was an evening assessment (from 19:01 until 03:00).
 
When not all parameters are available on a certain timepoint then following rules apply:
 
 - If temperature or oxygen saturation are available but not normalized then there is no resolution for this timepoint - If more than 2 parameters are not normalized then there is no resolution for this timepoint - If 4 parameters including temperature and oxygen saturation are normalized (allowing 1 missing parameter) then there is resolution for this timepoint. 
Else the resolution on this timepoint is missing
 
Subjects without postbaseline data are excluded.

--	---

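### Time to clinical response: at incomplete timepoints, two known abnormal values among heart rate, respiration rate and SBP are coded as missing, although the 4-of-5 definition already rules out resolution

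*SAP*

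**What the plan says.** Protocol 2.1.2 (repeated in 11.4) sets the endpoint: "Clinical response is defined as achieving 4 of the 5 following vital sign resolution criteria, including at least the fever and oxygen saturation criteria", held for at least 24 hours.

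SAP 5.3.1.1 turns this into a rule per timepoint and a rule for the run. A timepoint counts "where at least 4 of 5 symptoms (temperature, blood oxygen saturation, heart rate, SBP, respiration rate) are normalized", with temperature and saturation mandatory. The run is a "successive series of 4 recordings (over 5 scheduled successive analysis timepoints, 1 missing timepoint is allowed".

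The SAP then treats incomplete timepoints separately: "When not all parameters are available on a certain timepoint then following rules apply". There are three rules and a fallback:

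- Rule 1: "If temperature or oxygen saturation are available but not normalized then there is no resolution for this timepoint".
- Rule 2: "If more than 2 parameters are not normalized then there is no resolution for this timepoint".
- Rule 3: "If 4 parameters including temperature and oxygen saturation are normalized (allowing 1 missing parameter) then there is resolution for this timepoint".
- Fallback: "Else the resolution on this timepoint is missing".

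If response is never met, the censoring time depends on whether the last non-missing record shows normalization. If it does, censoring is at the first normalized record; if not, it is after the last observation.

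**The concern.** Rule 2 and the definition use different thresholds. If four of five must be normal, a second abnormal value settles the matter, whatever the unmeasured parameter would have shown. Rule 2 waits for a third. A timepoint with two known abnormal values that rule 1 does not catch is then treated as if nothing were known about it.

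The coding matters because missing and no resolution have different consequences. A timepoint with no resolution breaks a run; a missing one may be stepped over once. A recorded observation that disproves sustained response could therefore be skipped inside the run that is declared to be sustained response. It would also drop out of the record that decides where a non-responder is censored.

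The neighbouring rules show the expected logic. Rule 1 codes failure as soon as a mandatory parameter is known to be abnormal. The respiratory-response rule in the same section codes failure when one parameter is missing and the other is abnormal. Only rule 2 departs from this.

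**Working it through.** **1. Threshold implied by the definition.** With all five parameters measured, the patterns that resolve are: none abnormal, 1 of 1; one abnormal, 3 of 5 (the abnormal one must be heart rate, respiration rate or SBP); two abnormal, 0 of 10; three or more, 0 of 16. Failure is certain from two abnormal values on. The SAP's figure for incomplete timepoints is more than 2, that is, 3 or more.

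**2. Patterns affected.** Let each parameter be normal, abnormal or missing.

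- All patterns: 3^5 = 243. Complete: 2^5 = 32. Incomplete: 243 - 32 = 211.
- Incomplete with exactly two abnormal: 10 pairs x (2^3 - 1) = 70.
- Pair includes temperature or saturation: 7 pairs x 7 = 49. Rule 1 codes these correctly as no resolution.
- Pair lies within heart rate, respiration rate and SBP: 3 pairs x 7 = 21. Rule 1 does not apply, two is not more than two, and fewer than four are normal, so all 21 reach the fallback. Of these, 3 x 3 = 9 have only one parameter missing.

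A full enumeration compared the SAP code with what the definition forces over every possible completion of the missing values. As written, 21 of 211 patterns disagree, all coded missing where response is impossible. With a threshold of two, 0 of 211 disagree.

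Example: temperature 36.8 °C, saturation criterion met at 95% on room air, heart rate 125, respiration rate 32, SBP missing. Against SAP Table 4 (heart rate at most 100, respiration rate at most 24), at most three of five can be normal. The SAP codes this timepoint missing.

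**3. Effect on the run.** Illustrative clock times are 08:00, 12:00 and 20:00, with hours counted from the first timepoint:

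| Timepoint | Hours | Data | As written | Threshold 2 |
|---|---|---|---|---|
| 1 | 0 | not resolved | no | no |
| 2 | 4 | resolved | yes | yes |
| 3 | 12 | HR and RR abnormal, SBP missing | missing | no |
| 4 | 24 | resolved | yes | yes |
| 5 | 28 | resolved | yes | yes |
| 6 | 36 | resolved | yes | yes |
| 7 | 48 | resolved | yes | yes |

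As written, timepoints 2, 4, 5 and 6 are four recordings over five timepoints with one missing, so response is dated at 4 h. With a threshold of two, the run is 4 to 7 and response is dated at 24 h. If the subject is discharged after timepoint 6, there is an event at 4 h as written and a censored time after the correction. Recoding missing to no resolution can only break runs, so for event status and event time the present rule can only make response earlier or add an event.

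**4. Effect on censoring.** Suppose the miscoded timepoint is the last one and the record before it was normalized, without enough recordings for a response. As written, the last non-missing record is the normalized one, and censoring goes back to the first normalized record. Coded as no resolution, the subject would be censored after the last observation.

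**5. Frequency.** This cannot be derived from the documents. As an illustration, 100,000 subjects were simulated with 18 timepoints and vital signs recovering over 6 days, all assumed:

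| Missing per parameter | Timepoints miscoded | Subjects with at least one | Event time changed |
|---|---|---|---|
| 3% | 0.28% | 4.8% | 0.31% |
| 5% | 0.45% | 7.6% | 0.47% |
| 10% | 0.79% | 13.0% | 0.47% |

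On 600 subjects, the last column is 600 x 0.0031 = 1.9 to 600 x 0.0047 = 2.8, or about 2 to 3 subjects.

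**The case against.** The best defence is that rule 2, unlike rule 1, does not say the parameters must be available. If a missing value also counted as not normalized, two abnormal values plus a missing one would make three, and rule 2 would fire. This reading codes all 5 x 2^4 = 80 one-missing patterns correctly. It fails elsewhere. It turns 49 undetermined patterns, all with two or more parameters missing, into failures. One of these is the wholly unmeasured timepoint, which conflicts with the allowance for a missing timepoint in the run. Rule 1 also shows that the SAP distinguishes unavailable from not normalized. The reading does not rescue the rule, but it shows that the word available is needed in the correction.

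It is also fair to say that the skip is an inference. The SAP allows a missing timepoint in the run and separately codes a resolution as missing, without stating that the second fills the first. No other meaning is given, so this is the natural reading, but it is a reading.

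The assumed missingness may be unrealistic. Protocol 9.6.4 has blood pressure, pulse and respiratory rate taken with an automated device, so they may go missing together. That would make patterns such as the example rarer.

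A reader might infer that any timepoint with two abnormal vital signs is lost. The documents do not support that: complete timepoints follow the 4-of-5 definition directly, and rule 1 covers 49 of the 70 incomplete two-abnormal patterns.

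**Conclusion.** Rule 2 is wrong as written, within narrow limits: at least one parameter missing, temperature and saturation not known to be abnormal, and exactly two of heart rate, respiration rate and SBP known to be abnormal. In those 21 of 211 incomplete patterns the SAP's own definition rules out resolution and its rule returns missing. The consequence for response runs rests on treating a missing resolution as the allowed missing timepoint.

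Two stronger conclusions might be drawn and should not be. One is that the error always pushes towards response. That holds for event status and event time, but the censoring effect is an earlier censoring time, which is a different thing. Nor is any bias between arms shown, since the same rule applies to both blinded arms. The other is that a confirmatory claim is at risk. Time to clinical response is not among the seven endpoints in the hierarchy (Protocol 11.4, SAP 5.1.1), so type I error control and sample size are unaffected.

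The 0.3-0.5% of subjects with a changed event time illustrates the scale under assumed missingness; it is not an estimate for this trial. This is a minor correction that is worth making.

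**What to change.** In rule 2, replace the threshold of more than 2 parameters with *2 or more available parameters* and leave the rest of the sentence as it stands. The rule then agrees with the 4-of-5 definition in all 211 incomplete patterns.

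The word *available* is essential. Without it, a programmer who counted missing values as not normalized would code 71 undetermined patterns as failures, against 49 under the present threshold read that way.

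It would also help to state that a timepoint whose resolution is missing counts as the one missing timepoint allowed in the run.

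The cost is a few words in the SAP and one line of derivation code, applied identically to both arms.
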